#### **4.1.3 Ongoing Clinical Trials**

##### **4.1.3.1 PN069**

PN069 is a randomized, double-blind phase III study to evaluate the efficacy, safety and tolerability of MK-5592 IV solution and solid oral tablet (300 mg QD, 300 mg BID on Day 1 only) versus voriconazole IV and solid oral formulation [IV: 6 mg/kg BID for loading dose and 4 mg/kg BID for maintenance dose, solid oral formulation: 300 mg BID for loading dose and 200 mg BID for maintenance dose] for the treatment of invasive aspergillosis in adults;

[REDACTED]

[REDACTED]

cc1

).

## 4.2 Rationale

### 4.2.1 Rationale for the Trial and Selected Subject Population

The diagnosis of invasive fungal infections (IFI) is generally difficult and most of patients with IFI have serious underlying diseases. In most of cases the therapy for IFI is initiated prior to the diagnosis of IFI because the condition of patient is critical. The antifungal agents approved in Japan are not always effective depending on the IFI morbidity and it is reported that some patients displayed unfavorable response to the conventional medication. Therefore there are high medical needs to develop safe and effective antifungal agent with broad spectrum against fungi.

Amphotericin B has broad spectrum activity against fungi and has a strong antifungal activity, many adverse effects are observed due to strong toxicity. Antifungal agents such as azoles and echinocandins are superior to amphotericin B with regards to safety and pharmacokinetics profile, but antifungal spectrum is not entirely satisfactory.

MK-5592 is an antifungal agent in the azole class that inhibits ergosterol biosynthesis, a in the main component of the fungal cell membrane, by affecting the enzyme lanosterol 14-alpha demethylase (CYP51). Nonclinical and clinical studies (MK-5592 oral suspension) indicate that MK-5592 is effective against broad fungus including zygomycota that is refractory to voriconazole in addition to aspergillus. In safety profile, azole specific ADRs were observed, but well tolerated.

[figure not shown]
Based on the above, MK-5592 is expected to be safe and efficacious in the treatment of broad deep-seated fungal infections and should be considered as one option for the treatment of these deep-seated fungal infections to meet the current medical needs. This Phase 3 study is planned to assess the safety and efficacy of MK-5592 in patients with proven or probable deep-seated fungal infections in Japan using the criteria and endpoints referred to in the EORTC/MSG criteria [14, 15], endpoints of MK-5592 clinical study conducted outside Japan, endpoints of clinical study for chronic pulmonary aspergillosis conducted in and outside Japan [16, 17], and the guideline as antifungal drugs evaluation committee by Japan chemotherapy association March 2012 [18].

[figure not shown]
Details regarding specific benefits and risks for subjects participating in this clinical trial may be found in the accompanying Investigators Brochure (IB) and Informed Consent documents.

Subjects in clinical trials generally cannot expect to receive direct benefit from treatment during participation, as clinical trials are designed to provide information about the safety and effectiveness of an investigational medicine.

[figure not shown]
#### **4.2.2 Rationale for Dose Selection/Regimen/Modification**

##### **1) Rationale for MK-5592 dosage and administration**

**For Cohort 2**

2) Rationale for Voriconazole Dosage and Administration

Dosage of Voriconazole was chosen based on approved dosage of treatment for deep-seated fungal infection in Japan. Oral administration is 200 mg BID (300 mg BID on Day 1), IV infusion is 4 mg/kg BID (6 mg/kg BID on Day 1).

In JPC of voriconazole, ‘it is recommended that plasma concentration of voriconazole should be monitored during the treatment’ is stated. From the both efficacy and safety aspects, dosing adjustment based on the result of therapeutic drug monitoring (TDM) is recommended for voriconazole in Japan. Therefore, in this study, adjustment of voriconazole dosing should be performed based on the result of TDM, with the dose modified at the investigator’s discretion. The frequency of blood sampling for TDM is also left to the investigator’s discretion.

#### **4.2.3 Rationale for Endpoints**

Safety and efficacy endpoints in this study are based on the EORTC/MSG criteria [14, 15], endpoints of MK-5592 clinical study conducted outside Japan, endpoints of clinical study for chronic pulmonary aspergillosis conducted in and outside Japan [16, 17], and the guideline as antifungal drugs evaluation committee by Japan chemotherapy association March 2012 [18]. Deep-seated fungal infection is usually manifested in immunocompromised subjects with serious underlying diseases (such as HIV, organ transplantation, and cancer). For such infections, the assessment of efficacy usually takes into consideration a number of key variables, including the response to clinical signs and symptoms (Clinical Response), the response to mycological measures of the infection (Mycological Response), and the response to radiological evidence of the infection (Radiological Response). Therefore, an overall response, which encompasses many of these individual components, is routinely applied to the assessment of efficacy in these types of infections. Overall response criteria for invasive aspergillosis is set in 5 levels (complete response, partial response, stable response, progressive disease and unable to determine). Success is defined as complete response and partial response. Failure is defined as stable response, progressive disease and unable to determine. Overall response criteria for chronic pulmonary aspergillosis is set in 4 levels (favorable response, stable response, progressive disease and unable to determine). Success is defined as favorable response. Failure is defined as stable response, progressive disease and unable to determine. For chronic pulmonary aspergillosis, it is rare that ‘finding of imaging’ are resolved. Complete response and partial response are not set but favorable response is set in overall response. The overall response is evaluated by the investigator or sub-investigator according to the criteria. The overall response is finally evaluated by the clinical adjudication committee.

For subject with IA, we set the endpoint at Day 42 same as global study (069 study) in order to be able to confirm the efficacy between 101 and 069 study. For subject with CPA, we set the endpoint at Day 84 same as registration clinical studies conducted with using other anti-fungal drugs in the subject with CPA in Japan.

Pharmacokinetics endpoints were chosen to evaluate MK-5592 PK profile and will be able to compare to other clinical trials.

#### **4.2.3.1 Efficacy Endpoints**

##### **(1) Invasive aspergillosis**

Overall response for efficacy is evaluated based on clinical response, radiological response and mycological response.

##### **(2) Chronic pulmonary aspergillosis (chronic progressive pulmonary aspergillosis and simple pulmonary aspergilloma)**

Overall response for efficacy is evaluated based on clinical response, radiological response.

##### **(3) Fusariosis and Zygomycosis**

Overall response for efficacy is evaluated based on clinical response, radiological response and mycological response.

##### **(4) Antifungal susceptibility testing**

Minimum inhibitory concentration (MIC) of MK-5592, voriconazole and representative anti-mycosis drugs will be measured in the isolated causative fungus from the subjects (pre-treatment, post-treatment).

Individual evaluation criteria and overall response criteria is defined as follows;

#### **Criteria for Each Evaluation Element**

Table 7 Criteria for Clinical Response

Response	Definition
Resolution †	Resolution of attributable signs and symptoms of disease
Improvement	Improvement of attributable signs and symptoms of disease ‡
Stabilization	No change or minor improvement of attributable signs and symptoms of disease
Worsening	Worsening of attributable signs and symptoms of disease
Unable to Determine	Unable to determine
Clinical response is evaluated based on the clinical signs and symptoms related to mycosis (cough, dyspnea, sputum, hemoptysis, bloody sputum, pain, pyrexia and weight loss etc), with vital sign and shift of clinical laboratory (CRP etc) for reference during the trial.	
† : It does not use for chronic pulmonary aspergillosis	
‡ : “Resolution or Improvement of attributable signs and symptoms of disease” for chronic pulmonary aspergillosis	

Table 8 Criteria for the Radiological Response

Response	Definition
Resolution †	Resolution of radiological lesions
Improvement ‡	Major reduction of size of radiological lesions §
Stabilization	No change or minor reduction of size of radiological lesions
Worsening	Increase of size of existing lesion or new site with fungal infection
Unable to Determine	Unable to Determine

Imaging findings caused by fungus is evaluated.  
†: It does not use for chronic pulmonary aspergillosis  
‡: In the case of invasive aspergillosis, fusariosis, and mucormycosis, reduction of the longest diameter of lesions on imaging by 25% or more; for chronic pulmonary aspergillosis, whether lesions have been improved or not is judged by considering change in size and quality of lesions on imaging comprehensively.  
§: “Resolution or improvement of radiological lesions” for chronic pulmonary aspergillosis

Table 9 Criteria for Mycological Response

Response	Definition
Eradication	Fungus detected from culture or microscopy at the screening is eradicated at the time of evaluation(including presumed eradication † )
Stabilization	“Fungus detected from culture or microscopy at the screening is detected at the time of evaluation” or “Fungus at the screening is not detected at the time of screening and evaluation”
Worsening	Fungus is not detected at the screening but fungus or newly infected site is detected at the time of evaluation.
Unable to Determine	Unable to determine

†: It is difficult to obtain the sample due to eradication of infection site (etc.) but it is clinically judged to eradicate the infected fungus.

**Criteria for Overall Response**

Table 10 Overall Response Criteria for Invasive Aspergillosis, Zygomycosis and Fusariosis

		Clinical Response				
		Resolution	Improvement	Stabilization	Worsening	Unable to determine
Radiological Response	Resolution	Complete Response	Partial Response	Partial Response	Progressive Disease	Unable to determine
	Improvement	Partial Response	Partial Response	Partial Response	Progressive Disease	Unable to determine
	Stabilization	Partial Response	Partial Response † / Stable response †	Stable Response	Progressive Disease	Unable to determine
	Worsening	Progressive Disease	Progressive Disease	Progressive Disease	Progressive Disease	Progressive Disease
	Unable to determine	Unable to determine	Unable to determine	Unable to determine	Progressive Disease	Unable to determine

†: Assessment based on the Mycological Response in below

- In case of “Detected at Screening” and “Undetected at the Evaluation”, Mycological Response and Overall Response are “Resolution” and “Partial Response”, respectively.
- In case of “Undetected at Screening” and “Undetected at the Evaluation”, Mycological Response and Overall Response are “Stabilization” and “Stable Response”, respectively.
- In case of “Detected at Screening” and “Detected at the Evaluation”, Mycological Response and Overall Response are “Stabilization” and “Stable Response”, respectively.
- In case of “Undetected at Screening” and “Detected at the Evaluation”, Mycological Response and Overall Response are “Worsening” and “Stable Response”, respectively.

Table 11 Overall Response Criteria for Chronic Pulmonary Aspergillosis

		Clinical Response			
		Improvement	Stabilization	Worsening	Unable to determine
Radiological Response	Improvement	Favorable Response	Favorable Response	Progressive Disease	Unable to determine
	Stabilization	Favorable Response	Stable Response	Progressive Disease	Unable to determine
	Worsening	Progressive Disease	Progressive Disease	Progressive Disease	Progressive Disease
	Unable to determine	Unable to determine	Unable to determine	Progressive Disease	Unable to determine

Table 12 Overall Response Criteria for in Case of Zygomycosis and Fusariosis Without Imaging

		Clinical Response				
		Resolution	Improvement	Stabilization	Worsening	Unable to determine
Mycological Response	Eradication	Complete Response	Partial Response	Stable Response	Progressive Disease	Unable to determine
	Stabilization	Partial Response	Stable Response	Stable Response	Progressive Disease	Unable to determine
	Worsening	Progressive Disease				
	Unable to determine	Unable to determine	Unable to determine	Unable to determine	Progressive Disease	Unable to determine

#### 4.2.3.2 Safety Endpoints

Safety endpoints are evaluated based on physical findings, clinical symptoms and signs, vital signs, 12-lead ECG and laboratory measurements. Adverse events are collected through the study duration from the subjects.

#### 4.2.3.3 Pharmacokinetic Endpoints

Steady-state pharmacokinetic profile of MK-5592 in Japanese patients with mycosis will be explored using population PK approach. The PPK analysis plan will be prepared separately.

*For MK-5592 treatment arm, plasma samples for PK evaluation will be collected at the following time points:*

For IV administration: Thirty minutes before the treatment, just before the end of first infusion, 6 to 10 hours after the initiation of the infusion and just before the treatment of second infusion on Day 1[Blood sampling after the first dosing on Day 1 (or second dosing) should be performed at least 3 hours apart among these sampling points (6 to 10 hours after the treatment and just before the second treatment)]. Thirty minutes before the treatment on Day 3, 14, 28, 42 and end of treatmenta, b. Thirty minutes before the treatment, just before the end of the infusion, 2 to 3 hours after the initiation of infusion, 8 to 10 hours after the initiation of infusion on Day 8 and thirty minutes before the treatment of the next day (on Day 9).

For oral administration: Thirty minutes before the treatment, 2 to 4 hours after the first treatment, 6 to 10 hours after the treatment and just before the second treatment on Day 1[Blood sampling after the first dosing on Day 1 (or second dosing) should be performed at least 3 hours apart among these sampling points (6 to 10 hours after the treatment and just before the second treatment)]. Thirty minutes before the treatment on Day 3, 14, 28, 42 and end of treatmenta, b. 30 minutes before the treatment and 2 to 6 hours after the treatment on after 7 days of switching formulation (Only for the subjects who switch from IV to orala). Thirty minutes before the treatment, 2 to 3 hours after the treatment, 4 to 6 hours after the treatment, 8 to 10 hours after the treatment on Day 8 and 30 minutes before the treatment of the next day (on Day 9).

[figure not shown]
For both formulations: At the time of interruptiona or discontinuationa due to adverse events, or at the incidence of serious adverse eventsa by MK-5592 administration.

a: The plasma samples for PK evaluation in the subjects with zygomycosis during the extension period will not be needed.

b: The plasma samples for PK evaluation in the subjects with zygomycosis must be collected at EOT before the transition to the extension period.

#### **4.2.3.4 Future Biomedical Research**

The Sponsor will conduct Future Biomedical Research on DNA (blood) specimens collected during this clinical trial.

## **5.0 METHODOLOGY**

### **5.1 Entry Criteria**

#### **5.1.1 Diagnosis/Condition for Entry Into the Trial**

Male/Female subjects with deep-seated mycosis of at least 18 years of age will be enrolled in this trial.

### **5.1.2 Subject Inclusion Criteria**

In order to be eligible for participation in this trial, the subject must:

1. The subject whose written consent is obtained prior to the study. If the subject is incompetent, the written consent of an appropriate attorney\* must be obtained. If the subject is infirm, the written consent/assent of a subject and an appropriate attorney\* must be obtained. The subject may also provide consent/assent for Future Biomedical Research. However, the subject may participate in the main trial without participating in Future Biomedical Research.

\* Appropriate attorney includes those persons who can consider the best benefit of the subject judging from the livelihood or mental relationships with the subject, such as a spouse, parent, legal guardian or other person pursuant to those persons.

2. Male or female Japanese subject aged 18 years and over at the time when informed consent is obtained, and subject with body weight greater than or equal to 45 kg at the randomization.
3. The subject who can take investigational medical products [he/she can take tablet via oral or he/she can take IV formulation via central vein (he/she has central venous catheter or he/she can obtain a central venous catheter)]
4. The subject (only female) who has a negative pregnancy test at screening visit. Female subjects of child-bearing potential who agree to continue using proper combination of barrier method of birth control (e.g. condom, pessary, oral contraceptive, intrauterine device (IUD), hormonal implant, vasectomy) during the study period. Female subjects of non-child-bearing potential are defined as having none of following three items.
  - (1) 12 months of spontaneous amenorrhea with no alternative medical cause
  - (2) 6 month or more post surgical bilateral oophorectomy with or without hysterectomy
  - (3) Bilateral tubal ligation
5. As a result of screening test within 7 days prior to Day 1, subject met the following criteria for 1 of the 4 listed fungal infections.
  - (1) Invasive Aspergillosis

Subject meets the following criteria for proven, probable or possible IA

- (a) Proven IA: the subject meets the following criteria 1) or 2)

- 1) Tissue histopathologic, cytopathologic\*, or direct microscopic examination of a needle aspiration or biopsy specimen obtained within 14 days prior to Day 1 showing hyphal forms with evidence of associated tissue damage (either microscopically or as an infiltrate or lesion by imaging)

\*: tissue and cells submitted for histopathology or cytopathology should be stained by Grocott-Gomori methenamine silver stain or by periodic acid Schiff stain to facilitate inspection of fungal structures. Where possible, wet mounts of specimens from foci related to invasive fungal infectious disease should be stained with a fluorescent dye (e.g., calcofluor or Blankophor).

- 2) Recovery of Aspergillus species by culture from a sample obtained by a sterile procedure from a normally sterile and clinically or radiologically abnormal site consistent with an infectious disease process obtained within 14 days prior to Day 1, excluding BAL, cranial sinus cavity, and urine.

(b) Probable IA: the subject meets one host factor, one clinical criteria and one mycological criteria, respectively

- 1) Host factors\*

- i. Recent history of neutropenia ( $0.5 \times 10^9$  neutrophils/L [ $<500$  neutrophils/mm^3] for  $>10$  days) temporally related to the onset of fungal disease
- ii. Receipt of an allogeneic HSCT
- iii. Treatment with other recognized T-cell immune suppressants, such as cyclosporine, TNF- $\alpha$  blockers, specific monoclonal antibodies (such as alemtuzumab), or nucleoside analogues during the past 90 days.
- iv. Prolonged use corticosteroid (excluding among patients with allergic bronchopulmonary aspergillosis) at a mean minimum dose of 0.3 mg/kg/day of prednisone equivalent for  $>3$  weeks.
- v. Inherited severe immunodeficiency (such as chronic granulomatous disease or several combined immunodeficiency)

- vi. Host factor which matches to develop invasive aspergillosis (In this case the pre-approval of the sponsor is required and subject meets one clinical criteria and one mycological criteria)

\*: Host factors are not synonymous with risk factors and are characteristics by which individuals predisposed to invasive fungal

diseases can be recognized. They are intended primarily to apply to patients given treatment for malignant disease and to recipients of allogeneic hematopoietic stem cell and solid-organ transplants. These host factors are also applicable to patients who receive corticosteroids and other T cell suppressants as well as to patients with primary immunodeficiencies.

2) Clinical criteria\*

- i. For lower respiratory tract fungal disease\*\*, the presence of 1 of following 3 signs: 1) dense, well-circumscribed lesions(s) with or without a halo sign, 2) air-crescent sign or 3) cavity on CT
- ii. For tracheobronchitis, tracheobronchial ulceration, nodule, pseudomembrane, plaque, or eschar seen on bronchoscopic analysis
- iii. For sinonal infection, Imaging showing sinusitis plus at least 1 of the following 3 signs: 1) Acute localized pain (including pain radiating to the eye), 2) Nasal ulcer with black eschar or 3) Extension from the paranasal sinus across bony barriers, including into the orbit
- iv. CNS infection 1 of the following 2 signs: 1) Focal lesions on imaging, 2) Meningeal enhancement on MRI or CT

\* : Must be consistent with the mycological findings, if any, and must be temporally related to current episode.

\*\*: Every reasonable attempt should be made to exclude an alternative etiology.

3) Mycological criteria

- i. For direct test (cytology, direct microscopy, or culture), Mold in sputum, bronchoalveolar lavage fluid, bronchial brush, or sinus aspirate samples obtained within 14 days prior to Day 1, indicated by 1 of the following: 1) Presence of fungal elements indicating a mold or 2) Recovery by culture of a mold (e.g., Aspergillus species)
- ii. For indirect tests (detection of antigen or cell-wall constituents), Galactomannan antigen detected in serum or bronchoalveolar lavage (BAL) fluid [a positive test result defined as a cut-off index  $\geq 1.0$  (single result from serum or BAL) or  $\geq 0.5$  (2 consecutive results from serum samples)]

(c) Possible IA: the subject meets one host factor (vi is not applicable for this criteria) and one clinical criteria, respectively. Of the subject who is enrolled as possible IA, if the subject meets the criteria for proven IA or probable IA

within 7 days of randomization, it is treated as proven IA or probable IA respectively.

(2) Chronic pulmonary aspergillosis (chronic progressive pulmonary aspergillosis or simple pulmonary aspergilloma)

The subject meets host factor, clinical criteria and mycological criteria with active chronic pulmonary aspergillosis.

(a) Host factors:

The subject has one of the risk factor of chronic pulmonary aspergillosis (chronic progressive pulmonary aspergillosis or simple pulmonary aspergilloma) (obsolete pulmonary tuberculosis, COPD, bronchiectasis, cavity formulation including cyst, pulmonary nontuberculous mycobacteriosis, interstitial pneumonia or history of chest surgery etc)

(b) Clinical criteria: subject meets the all of following criteria

- 1) The subject has attributable chronic signs and symptoms [e.g. cough, sputum (bloody sputum or hemoptysis etc), dyspnea, pyrexia, weight decrease etc]
- 2) The subject has a shadow [enhancement of cavity, thickness of cavity wall (enhancement of cavity consolidation), fungus ball-like shadow, progression of pleural thickening or niveau etc.] by chest imaging (CT) and it is judged that other causes are negative.

(c) Mycological criteria: the subject meets one of following criteria by mycological testing or serological testing

- 1) Fungal element of Aspergillus species is detected by direct microscopy in biopsy specimen (bronchial mucosa or lung etc.), BAL, sputum, sputum with transtracheal aspiration, pleural effusion or a sample obtained within 14 days prior to Day 1 using any other appropriate method, or recovery of Aspergillus species by culture of samples obtained within 14 days prior to Day 1 (Proven case)
- 2) Aspergillus species is detected by histopathological testing of samples obtained within 14 days prior to Day 1 (Proven case)
- 3) Galactomannan antigen is detected in serum or bronchoalveolar lavage (BAL) fluid [a positive test result defined as a cut-off index  $\geq 1.0$  (single result from serum or BAL) or  $\geq 0.5$  (2 consecutive results from serum samples)], or aspergillus antibody is detected in serum or BAL (Probable case) Aspergillus antibody within 28 days before the initiation of study therapy, it can be used as a screening result.

- (3) Zygomycosis (The subject is assigned to the MK-5592 treatment arm); Fungal infection is strongly suspected based on clinical symptom and/or characteristic imaging findings and meets at least one of the following criteria: If data of (a) and (b) comes from within 14 days before initiation of study therapy, it can be used as a screening result.
  - (a) Fungal elements of *Zygomycota* spp (*Rhizopus*, *Absidia*, *Rhizomucor*, *Mucor*, *Cunninghamella*, etc.) mold in biopsy sample (bronchial mucosa, lung etc.), broncho-aleveolar lavage fluid, sputum, sputum with transtracheal aspiration, pleural effusion, blood and any other appropriate sample by direct microscopy or *Zygomycota* spp. are observed by culture test.
  - (b) *Zygomycota* spp. is detected by histopathologic test.
- (4) Fusariosis (The subject is assigned to the MK-5592 treatment arm); Fungal infection is strongly suspected based on clinical symptom and/or characteristic imaging findings etc. and met at least one of the following criteria: If data of (a) and (b) comes from within 14 days before initiation of study therapy, it can be used as a screening result.
  - (a) Fungal elements of *Fusarium* spp. mold in biopsy sample (bronchial mucosa, lung etc.), broncho-aleveolar lavage fluid, sputum, sputum with transtracheal aspiration, pleural effusion, blood and any other appropriate sample by direct microscopy or *Fusarium* spp. are observed by culture test.
  - (b) *Fusarium* spp. is detected by histopathologic test.

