## 6.0 TRIAL FLOW CHART

Trial Period:	Screening	Treatment								Post-treatment	Extension 
		In-patient 			In-patient/Out-patient						In-patient/ Out-patient
Visit Number/Title:	1 Screening	2 Day 1	3 Day 3	4 Day 8	5-8 After Day 8	9 Day 42	10, 11 After Day 42	12 End of treatment or discon 	X Day of formulation switch	13 14 days after end of treatment	X
Scheduled Day.:	-7 to -1	1	3	8	14, 21, 28, 35	42	56, 70	84	X	14	X
Scheduling Window Days	-	-	+2	+/-1	+/-3	-3 to +7	+/-6	+2	-1	+7	-
Administrative Procedures											
Informed Consent	x 										
Informed Consent for Future Biomedical Research	x										
Subject Identification Card	x										
Inclusion/Exclusion Criteria	x										
Medical History	x										
Prior and Concomitant Medication Review	x	Continuing to confirm									
Physical Examination (clinical finding)	x	x 	x	x	x	x	x	x	x	x	
Assessment of Clinical signs and symptom of deep-seated mycosis	x	x 	x	x	x	x	x	x	x	x	
Vital signs and weight	x	x 	x	x	x	x	x	x	x	x	
Height	x										
12-Lead Electrocardiogram 	x	x	x	x		x		x	x	x	
Diagnostic imaging (CT, MRI etc.)	x 					x		x	x	x	
Mycology test (culture testing, direct microscopy or histopathological examination etc.) 	x 					x		x		x	
Serology testing 	x 		x 			x		x	x	x	
Hematology	x	x 	x	x	x	x	x	x	x	x	
Serum Chemistry	x	x 	x	x	x	x	x	x	x	x	
Serum Pregnancy testing (only for potency of child-bearing female)	x 					x		x			
Treatment Allocation/Randomization		x 									
Collection of sample to measure MK-5592 plasma concentration (MK-5592 treatment arm) 		x	x	x	x	x		x	x 		
Blood for Future Biomedical Research 		x									
MK-5592, Voriconazole Administration		Everyday									x
Switching the formulation of study drug 									x		

Trial Period:	Screening	Treatment								Post-treatment	Extension 
		In-patient 			In-patient/Out-patient						In-patient/Out-patient
Visit Number/Title:	1 Screening	2 Day 1	3 Day 3	4 Day 8	5-8 After Day 8	9 Day 42	10, 11 After Day 42	12 End of treatment or discon 	X Day of formulation switch	13 14 days after end of treatment	X
Scheduled Day.:	-7 to -1	1	3	8	14, 21, 28, 35	42	56, 70	84	X	14	X

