#### **7.1.3.1 Laboratory Safety Evaluations (Hematology, Chemistry and Urinalysis)**

Laboratory tests for hematology, chemistry are specified in [Table 20](#) to [Table 22](#).

Table 20 Laboratory Tests (Hematology)

Red blood cell count (RBC)
Hemoglobin
Hematocrit
Platelet count
White blood cell count (WBC)
WBC differential (neutrophil, eosinophil, basophil, lymphocyte, monocyte)

Table 21 Laboratory Tests (Blood Chemistry)

Total protein	Blood Urea Nitrogen
Albumin	Creatinine
Aspartate aminotransferase (AST)	Uric acid
Alanine aminotransferase (ALT)	CRP
Alkaline phosphatase	Calcium
LDH	Chloride
Total Bilirubin	Potassium
Direct Bilirubin	Sodium
	Magnesium

Table 22 Laboratory Test (Other)

Serum hCG (Total hCG or $\beta$ -hCG): female subjects of childbearing potential
Aspergillus antibody (only for subject with Chronic pulmonary aspergillosis): perform at Screening visit only
Galactomannan antigen (ELISA): perform for the subject with aspergillosis only
$\beta$ -D-Glucan: perform for the subject with aspergillosis only

Serum electrolytes (K, Ca, Mg) must be measured on the same day and recorded in the source document and eCRF, in case an unscheduled 12-lead electrocardiogram is performed. In case adrenal insufficiency is observed, serum electrolytes (K, Ca, Mg) must be measured, evaluated and recorded in the source documents and eCRF.

If CRP is measured at the unscheduled visit, all of these data are recorded in the source document and eCRF appropriately.

Urine pregnancy testing can be conducted for confirmation of subject eligibility and it is not required to record in the eCRF. Even though urine pregnancy testing is conducted, serum pregnancy testing should be conducted as a screening testing and it is recorded in the source document and eCRF appropriately.

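### Inclusion criterion 4 defines non-child-bearing potential the wrong way round, so read literally the contraception condition and on-treatment hCG tests miss the women who can conceive

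*Combined protocol and SAP*

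**What the plan says.** Criterion 4 in Section 5.1.2 has three parts.

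- A test at entry for all women: "The subject (only female) who has a negative pregnancy test at screening visit".
- A contraception condition for one group only: "Female subjects of child-bearing potential who agree to continue using proper combination of barrier method of birth control".
- A definition of the complementary group: "Female subjects of non-child-bearing potential are defined as having none of following three items". The items are (1) "12 months of spontaneous amenorrhea with no alternative medical cause", (2) "6 month or more post surgical bilateral oophorectomy with or without hysterectomy" and (3) "Bilateral tubal ligation".

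Two other places rely on the same classification without defining it. The serum pregnancy test row of the flow chart (Section 6.0), marked at screening, Day 42 and end of treatment, is limited to women of child-bearing potential. Table 22 (Section 7.1.3.1) restricts serum hCG to "female subjects of childbearing potential".

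**The concern.** A definition of women who cannot conceive should be met by having one of the listed states, not by having none of them. As worded, the criterion puts fertile women in the exempt group and women past menopause or surgically sterilised in the group that must use contraception and be tested.

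At stake are the two measures that operate during treatment: the contraception condition and the scheduled hCG tests at Day 42 and end of treatment. A site that follows the text exactly withdraws both from the women they are meant to protect, over as much as 84 days of azole treatment. The same site would also have to treat a post-menopausal woman who does not use contraception as failing an inclusion criterion. A site that applies the evident intention departs from a written eligibility rule, although the code of conduct in Section 12.1 requires subjects to meet the entry criteria.

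**Working it through.** The point is one of logic, so the check sets out the definition and then traces what depends on it. There is no figure in the plan to reproduce.

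**Step 1. The definition.** Let A, B and C stand for items (1), (2) and (3), each true or false for a given woman.

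- As written: non-child-bearing = not A and not B and not C.
- As the list implies, since each item is a state in which conception is not expected: non-child-bearing = A or B or C.

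The second expression is the exact negation of the first. Over the 2 × 2 × 2 = 8 combinations:

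| Items present | Combinations | Class as written | Class implied by the list |
|---|---|---|---|
| None | 1 | Non-child-bearing | Child-bearing |
| At least one | 7 | Child-bearing | Non-child-bearing |

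The two readings agree in 0 of 8 combinations and disagree in 1 + 7 = 8. The definition is fully inverted; this is not a matter of a few borderline cases.

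**Step 2. Is there another definition?** None was found. The flow chart and Table 22 use the term but do not define it, so a reader looking for its meaning has only criterion 4.

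**Step 3. What depends on the term.**

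| Requirement | Where | Who is covered | Effect of the literal text on a fertile woman |
|---|---|---|---|
| Contraception during the study | 5.1.2, criterion 4 | Child-bearing potential only | Lapses |
| Serum hCG at Day 42 and end of treatment | 6.0; Table 22 | Child-bearing potential only | Lapses |
| Negative pregnancy test at screening | 5.1.2, criterion 4, first sentence | Every woman | Stays |
| Exclusion if pregnant, nursing, or intending pregnancy | 5.1.3, criterion 20 | Every woman | Stays |

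The flow chart also limits the screening serum test to women of child-bearing potential, but the first sentence of criterion 4 independently requires a negative screening result from every woman. Screening is therefore not lost.

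**Step 4. Does anything else fill the gap during treatment?** Section 5.8 names pregnancy as an example of a reason for discontinuation, and Section 7.2.2 requires pregnancies to be reported within 24 hours and followed to outcome. Section 7.2.2 covers pregnancies that come to the investigator's notice spontaneously and schedules no test. The Day 42 and end-of-treatment hCG tests are the only scheduled detection after entry, and both depend on the inverted term.

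**The case against.** The strongest reply is that the slip reveals itself. Only the non-child-bearing group is defined; child-bearing potential is never defined directly and can be read in its ordinary sense wherever a requirement uses it. To reach the harmful result, a site would have to class a woman without ovaries as able to conceive, with the list printed directly beneath the sentence. Other controls also remain: the screening test, exclusion criterion 20, investigator judgement of fitness under exclusion criterion 22, discontinuation and reporting of pregnancy, and, in the voriconazole arm, the Table 19 advice on additional contraception when oral contraceptives are used. The documents give no sex or age distribution, so exposure cannot be sized. Nothing in the sample size, endpoints or analysis changes.

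Much of this stands. Misapplication is probably uncommon, the documents show no evidence of harm, and this is an internal inconsistency rather than a deliberate design choice. The flow chart and Table 22 are not themselves wrong.

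It does not remove the point. The entry safeguards act before treatment, and the discontinuation and reporting rules act once a pregnancy is known. Table 19 concerns only women already taking oral contraceptives in one arm. None of these sets a general contraception condition or schedules a test during treatment. An eligibility criterion should not have to be read as the opposite of what it says.

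**Conclusion.** The concern holds. The definition in criterion 4 is inverted in all 8 combinations of its items. Applied literally, it takes fertile women out of the contraception condition and the Day 42 and end-of-treatment hCG tests, and brings women not expected to conceive into both. Screening and the exclusion of pregnant women are unaffected.

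This rests on two assumptions: that the three items are meant as markers of not being able to conceive, and that child-bearing potential is the complement of the defined group. Every female participant would be placed in the group opposite to the one the list implies, but only if a site applies the sentence word for word. How many women that would be cannot be derived from the documents. The sponsor should correct it, on grounds of subject protection and clear eligibility; no statistical result depends on it.

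**What to change.** Reconcile the sentence in criterion 4 with its own list. Two one-word changes are logically equivalent: define women of non-child-bearing potential as having at least one of the three items, or delete the prefix so that women of child-bearing potential are those with none. The sponsor should confirm that the list itself is as intended.

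The flow chart and Table 22 need no new rule once criterion 4 is right; a cross-reference to the corrected definition would keep the three places aligned.

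The cost is a one-word correction in a protocol clarification letter or the next amendment. Visits, sample size and analysis do not change.
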